#### 3.4.2 ANALYSIS OF THE PRIMARY ENDPOINT

Success or failure of the study will be based on the primary effectiveness and safety endpoints, with descriptive assessment of the secondary safety endpoints. The primary effectiveness endpoint of Clinical Success will be assessed for all Target Lesions in the Completed Cases dataset and will be calculated on a per lesion basis.

$H_0: P_E \leq PG_E$ , versus

$H_A: P_E > PG_E$

Where  $P_E$  is the proportion of Target Lesions with Clinical Success and  $PG_E$  is the effectiveness performance goal of 72%.

The primary safety endpoint of freedom from major adverse events will be assessed for all subjects in the ITT population. The null and alternative statistical hypotheses for the primary safety endpoint will be defined as follows:

$H_0: Ps \leq PG_s$  versus

$H_A: Ps > PG_s$ ,

where  $Ps$  is the population primary safety success rate in the Test group and  $PG_s$  is the safety performance goal.

The study will be deemed successful if both the primary effectiveness and primary safety hypotheses are met. For the primary effectiveness endpoint, the lower limit of the one-sided 97.5% confidence interval must be greater than 72%. For the primary safety endpoint, the lower limit of one-sided 97.5% confidence interval must be great than 82%. Handling of missing data is described in section 3.4.1.

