Exclusion Criteria:	
The prospective study participant must not have any of the following exclusion criteria present at the time of eligibility assessment:
 
 
1. Pregnancy or breast feeding. A woman who, in the Investigator's opinion, is of child-bearing potential must have a negative pregnancy test within 7 days before the index procedure;
 

	
 
2. Coexisting signs of peritonitis or other active infection;
 
3. Participation in an investigational study of a new drug, biologic or device that has not reached its primary endpoint at the time of study screening;
 
4. Uncorrectable coagulopathies such as thrombocytopenia <40,000/<math>\mu</math>L, international normalization ratio (INR) >2.0;
 
5. Contraindication to angiography or catheterization, including untreatable allergy to iodinated contrast media;
 
6. Anatomic arterial unsuitability such that, in the Investigator's opinion, the delivery catheter cannot gain access to the selected position for safe and intended embolization;
 
7. Known allergy or other contraindication to any components of Lava LES including dimethyl sulfoxide (DMSO);
 
8. More than 4 Target Lesions will require embolization, in the Investigator's opinion after performance of diagnostic angiography or another suitable imaging study.
 

Performance Goal	
A 72% literature-derived performance goal was established for the primary effectiveness endpoint of 30-day Clinical Success.
 
An 82% literature-derived performance goal was established for the primary safety endpoint of freedom from 30-day major adverse events (defined as a composite of five events).

Study Hypothesis Testing	
The proportion of Target Lesions with 30-day Clinical Success will be tested against the 72% performance goal using a one-sided exact confidence interval with a one-sided alpha level of 0.025.
 
The proportion of patients experiencing freedom from 30-day major adverse events will be tested against the 82% performance goal using a one-sided exact confidence interval with a one-sided alpha level of 0.025.

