## 5.3 Secondary Endpoints

The following measures will be assessed as secondary endpoints of the study:

1. Technical Success, defined as absence of angiographic evidence of bleeding from the target lesion at the conclusion of the index procedure;
2. Successful delivery of Lava and intact retrieval of the microcatheter;
3. Assessment of each element of the primary safety endpoint (MAE) as an individual component;
4. Symptomatic ischemia in the target territory that does not require intervention;
5. All-cause mortality;
6. Bleeding-related mortality (attributable to bleeding in a target territory);
7. Open surgical conversion for persistent or recurrent bleeding;
8. Device-related serious adverse events;
9. Procedure-related serious adverse events;
10. Access site hematoma (>5cm in longest axis);c
11. Access site false aneurysm;
12. Units of red blood cells transfused after administration of Lava;

a The effectiveness endpoint is lesion-based and not subject-based. Failure of the effectiveness endpoint is triggered by events that are referable to the specific lesion and not to other events referable to another lesion in the same subject. For example, if a subject has two lesions where the first is treated successfully but the other rebleeds and requires emergency surgery, effectiveness would have been achieved in the first lesion but not in the second.

b Core laboratory-determined assessment of bleeding is used for the primary and secondary endpoints. If core laboratory images are unavailable or uninterpretable, the site-reported determinations will be used.

c As measured on a duplex ultrasound study, assessed by the Core Laboratory.

- 13. Duration index procedure, total and after administration of Lava;
- 14. Contrast administered during index procedure;
- 15. Fluoroscopy time during index procedure;
- 16. Length of stay in the intensive care unit after the index procedure;
- 17. Length of hospitalization, total and after the index procedure.

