## 7.10 Study Hypotheses

Success or failure of the study will be based on the primary effectiveness and safety endpoints, with descriptive assessment of the primary and secondary safety endpoints. The primary effectiveness endpoint of Clinical Success will be assessed for all Target Lesions in the Completed Cases dataset and will be calculated on a per lesion basis.

$H_0: P_E \leq PG_E$ , versus

$H_A: P_E > PG_E$

Where  $P_E$  is the proportion of Target Lesions with Clinical Success and  $PG_E$  is the effectiveness performance goal (**Section 7.8.2**).

The primary safety endpoint of freedom from major adverse events will be assessed for all subjects in the ITT population. The null and alternative statistical hypotheses for the primary safety endpoint will be defined as follows:

$H_0: Ps \leq PG_S$  versus  $H_A: Ps > PG_S$ ,

where  $Ps$  is the population primary safety success rate in the Test group and  $PG_S$  is the safety performance goal.

The study will be considered a success if the primary effectiveness and primary safety endpoints meets their respective performance goals, translating into the observation of a one-sided 97.5% lower confidence limits of the point estimate above 72% and 82%, respectively.

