### 8.3 Target Lesions, Vessels, and Territories

The Target Lesion is specified by the Investigator at the index procedure, after diagnostic angiography but prior to embolization, and is defined as a hemorrhage site planned for embolization with the Lava LES. Up to 4 Target Lesions may be treated in a subject.

Target Vessels are arteries where the tip of the delivery catheter is located at the time Lava administration is planned.k More than one Target Vessel may supply a single Target Lesion. Each Target Lesion is linked to a Target Territory, where the Target Territory is defined as the vascular territory supplied by a Target Vessel, within a single organ, extremity, or tissue bed.l

Non-Target Embolization is defined when Lava is unintentionally administered to a vascular bed outside a Target Territory. Non-target territory is defined as the vascular territory outside of the planned Target Territory specified by the Investigator prior to embolization at that site. Inadvertent embolization of Lava to a Non-Target Territory is an element of the composite MAE endpoint.

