## 1 PROTOCOL SUMMARY

### 1.1 SYNOPSIS

Title:	Liquid Embolization of Arterial Hemorrhages in the Peripheral Vasculature The LAVA Study
Study Description:	This statistical analysis plan (SAP) is for a prospective, multicenter, single-arm study of the Lava™ Liquid Embolic System (LES) for the embolic treatment of arterial hemorrhage in the peripheral vasculature compared to performance goals.
Objectives:	To evaluate the safety and effectiveness of the Lava LES for the embolic treatment of arterial hemorrhage in the peripheral vasculature. The study will test the proportion of Target Lesions with 30-day Clinical Success against a 72% performance goal and test the proportion of subjects experiencing freedom from 30-day major adverse events against a 82% performance goal both tests using a one-sided exact confidence interval and one-sided alpha level of 0.025.
Endpoints:	
Primary Safety Endpoint:
 
The primary safety endpoint is a composite of freedom from 30-day Major Adverse Events (MAEs). MAEs include the following events as adjudicated by an independent Clinical Events Committee (CEC):
 

1. Ischemia or infarction of the target territory;

2. Non-target embolization;

3. Allergic reactions to Lava;

4. Catheter breakage;

5. Catheter entrapment defined as the inability to withdraw a catheter from adherence to Lava.

 
Primary Effectiveness Endpoint:
 
The primary effectiveness endpoint is Clinical Success, defined as absence of bleeding from the target lesion after embolization with the Lava LES, without the need for emergency surgery, re-embolization, or other target lesion reinterventions within 30 days of the index procedure. Absence of bleeding is defined as no BARC Type 3 or greater bleeding occurring after the index procedure, either persistent or recurrent.

Study Population:	The study will enroll 113 male and female US subjects at least 18 years of age with active arterial bleeding from the peripheral vasculature, excluding those with bleeding from the vessels of the heart, intracranial vasculature, intra-dural bleeding in the spinal canal, and post-partum hemorrhage.
Phase:	This is a pivotal Investigational Device Exemption (IDE) study.

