### 3 STATISTICAL CONSIDERATIONS

#### 3.1 STATISTICAL HYPOTHESES

Success or failure of the study will be based on the primary effectiveness and safety endpoints, with descriptive assessment of the secondary safety endpoints.

The primary effectiveness endpoint of Clinical Success will be assessed for all Target Lesions in the Completed Cases dataset and will be calculated on a per lesion basis.

$H_0: P_E \leq PG_E$ , versus

$H_A: P_E > PG_E$ ,

where  $P_E$  is the proportion of Target Lesions with Clinical Success and  $PG_E$  is the effectiveness performance goal of 72%.

The primary safety endpoint of freedom from major adverse events will be assessed for all subjects in the ITT population. The null and alternative statistical hypotheses for the primary safety endpoint will be defined as follows:

$H_0: Ps \leq PG_S$  versus

$H_A: Ps > PG_S$ ,

 As measured on a duplex ultrasound study, assessed by the Core Laboratory.

where  $P_s$  is the population primary safety success rate in the Test group and  $PG_s$  is the safety performance goal of 82%.

The study will be deemed successful if both the primary effectiveness and primary safety hypotheses are met. For the primary effectiveness endpoint, the lower limit of the one-sided 97.5% confidence interval must be greater than 72%. For the primary safety endpoint, the lower limit of one-sided 97.5% confidence interval must be greater than 82%.

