### **Handling of Missing Data**

All attempts will be made to limit the amount of missing data. For all analyses of the primary endpoints, the number of observations available will be reported so the reader can assess the impact of missing data. In general, and for the primary endpoint analyses, missing data will not be imputed and analyses will be based on available data. For missing values on the primary safety endpoint, an adjustment to the denominator will be made based on the amount of evaluable data. For each visit (or reporting time point), the occurrence rate will be calculated as the number of subjects with certain endpoint occurrence term over the number of evaluable subjects. The evaluable subjects at each reporting time point include all subjects who are enrolled by the snapshot date and

- 1) had an endpoint occurrence within (on or before) the reporting cutoff days (30 days), or
- 2) had a follow-up at or after the lower limit of the reporting window (23 days), or
- 3) the withdrawal consent date/recorded lost-to-follow-up date at or after the lower limit of the reporting window.

Sensitivity analyses will be performed to assess the impact of missing data and potential correlation in the data for the primary endpoints. Three different sensitivity analysis are planned: (1) As described in the protocol, Target Lesions with unavailable effectiveness data will be assumed to have missing data at random and will be imputed by random selection with replacement of data from Target Lesions with complete data. (2) A tipping point analysis will be conducted in which lesions or subjects censored without an event prior to 30 days follow-up are sequentially imputed as failures at the time of censoring. (3) A generalized estimating equation (GEE) logistic regression model will be used to estimate clinical success taking into account potential correlation of multiple Target Lesions within a subject using an exchangeable working correlation structure. The analyses for all the secondary endpoints will not include imputation for missing data, and no formal statistical hypotheses will be tested.

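### The effectiveness decision limit treats Target Lesions as independent although a subject may have up to four, so the one-sided 0.025 level is not assured

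*SAP*

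**What the plan says.** The unit of analysis is the lesion. SAP 3.4.2 states that Clinical Success "will be assessed for all Target Lesions in the Completed Cases dataset and will be calculated on a per lesion basis". Footnote a of the protocol's endpoint section confirms this: "Failure of the effectiveness endpoint is triggered by events that are referable to the specific lesion". Protocol 8.3 adds: "Up to 4 Target Lesions may be treated in a subject".

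The study succeeds on effectiveness if a one-sided 97.5% lower limit exceeds 72% (SAP 3.1 and 3.4.2; Protocol 7.4 and 7.10). SAP 3.4.2 does not name the method, but both synopses do. The SAP describes "both tests using a one-sided exact confidence interval and one-sided alpha level of 0.025". The protocol says: "The proportion of Target Lesions with 30-day Clinical Success will be tested against the 72% performance goal using a one-sided exact confidence interval".

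Clustering appears once, in SAP 3.4.1 under Handling of Missing Data. The third of three sensitivity analyses is a GEE logistic model for "potential correlation of multiple Target Lesions within a subject using an exchangeable working correlation structure". Nothing connects its result to the success rule.

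The sample size (SAP 3.2, Protocol 7.9) is 101 Target Lesions from an exact binomial test, raised to 113 for 10% attrition. The text calls the 113 subjects. Protocol Table 5 and SAP Table 2 call them Target Lesions.

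**The concern.** Lesions in one person share coagulation status, the operator and the cause of bleeding. If their outcomes are positively correlated, the lesion proportion varies more than the binomial formula allows. The exact limit then sits too high, and at a true lesion rate of 72% the study could pass more often than 2.5% of the time on a pivotal endpoint. If the exact limit passed and the GEE did not, the plan as written would still declare success.

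The 101-lesion calculation makes the same independence assumption and states no number of lesions per subject. If the target were met in lesions rather than subjects, fewer subjects would supply them and clustering would be heavier.

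**Working it through.** **Inputs from the documents.** Null rate 72%, anticipated rate 84%, one-sided 0.025, exact binomial test, 101 Target Lesions, 10% attrition, at most 4 lesions per subject.

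**Reproducing the plan's figure.** The cut-off is the smallest r with P(X ≥ r | n, 0.72) ≤ 0.025. The smallest n with power of at least 80% at 84% is 101, with r = 82, actual level 0.0227 and power 0.819. The exact lower limit is 72.2% at 82/101 and 71.1% at 81/101. Then 101/0.9 = 112.2, rounded up to 113. The stated figures are correct for independent lesions.

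**Assumptions the documents do not supply.** Each mix has 101 evaluable subjects. Within-subject correlation is ρ.

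| Mix | Subjects with 1/2/3/4 lesions | Lesions | Exact cut-off |
|---|---|---|---|
| A | 101/0/0/0 | 101 | 82 |
| B | 91/10/0/0 | 111 | 90 |
| C | 81/12/6/2 | 131 | 105 |
| D (stress case) | 61/20/10/10 | 171 | 135 |

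**Variance inflation.** With m lesions in a subject, the design effect is 1 + (Σm²/Σm − 1)ρ. For C, Σm² = 81 + 48 + 54 + 32 = 215 and 215/131 = 1.641, so at ρ = 0.3 it is 1 + 0.641 × 0.3 = 1.19. For D, 391/171 = 2.287 gives 1.39. For B, 131/111 = 1.180 gives 1.05.

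**Actual level of the exact rule at a true rate of 72%.** Each subject's successes are beta-binomial with correlation ρ. They are convolved over subjects and the tail is taken from the cut-off.

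| Mix | ρ = 0.1 | 0.3 | 0.5 | 0.8 |
|---|---|---|---|---|
| A | 0.0227 | 0.0227 | 0.0227 | 0.0227 |
| B | 0.0194 | 0.0211 | 0.0229 | 0.0256 |
| C | 0.0244 | 0.0312 | 0.0382 | 0.0492 |
| D | 0.0311 | 0.0463 | 0.0616 | 0.0837 |

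**If 101 counts lesions from fewer subjects.** With 67 subjects (42/18/5/2), the rule of 82/101 has level 0.027, 0.038 and 0.048 at ρ = 0.1, 0.3 and 0.5.

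**A subject-clustered limit.** Let p be the plain lesion proportion, y the successes and m the lesions in each subject, N the total lesions and K the subjects. The robust variance is [K/(K−1)] × Σ(y − mp)²/N². The limit is taken on the logit scale with t on K−1 degrees of freedom. Results are from 60,000 simulated trials per cell (standard error of the level about 0.0006).

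| Mix | Level at ρ = 0.1/0.3/0.5/0.8 | Power at 84%, clustered limit | Power at 84%, exact rule |
|---|---|---|---|
| B | 0.020/0.020/0.020/0.022 | 0.83/0.82/0.80/0.78 | 0.83/0.83/0.82/0.82 |
| C | 0.021/0.022/0.023/0.025 | 0.87/0.83/0.78/0.71 | 0.90/0.88/0.87/0.86 |
| D | 0.024/0.025/0.024/0.025 | 0.93/0.87/0.80/0.70 | 0.96/0.94/0.93/0.90 |

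In mix A the clustered limit has the same cut-off as the exact rule: 82/101 gives 72.2% and passes, 81/101 gives 71.1% and fails.

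**Why not promote the planned exchangeable GEE.** It gives less weight per lesion to multi-lesion subjects, so it does not target the plain lesion proportion when lesion count is related to outcome. Take mix C with 76% success in single-lesion and 65.5% in multi-lesion subjects. The overall rate is (81 × 0.76 + 50 × 0.655)/131 = 72%. At ρ = 0.1/0.3/0.5/0.8 the exchangeable GEE has level 0.029/0.040/0.048/0.052, against 0.021/0.021/0.022/0.023 for the independence-working robust limit.

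**The case against.** The strongest reply is that the defect is conditional and partly anticipated. The SAP already prespecifies a GEE, four lesions is a ceiling rather than an expectation, and using 113 for both subjects and lesions fits roughly one lesion each. Several Target Vessels may feed one Target Lesion (Protocol 8.3), so multi-vessel embolization need not create several lesions. No passage supports a mix as heavy as D. This stands as a limit on the size of the problem, and D should be read only as a stress case.

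It is also true that the correlation at which 0.025 is first exceeded depends heavily on binomial discreteness at the chosen lesion total. With 20 two-lesion subjects among 101 (121 lesions), the level stays below 0.025 up to ρ = 0.5 (0.0224). With a lighter mix of 92/7/1/1 (113 lesions), it is 0.0263 already at ρ = 0.1. No single threshold correlation should therefore be quoted.

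The documents do not settle how large the correlation is. Scoring failure by lesion argues against a very high value. On the other side, the BARC Type 3 criteria in Protocol section 18 include hemoglobin drop and vasoactive drugs, which are measured on the subject, and bleeding is defined there by target territory.

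Finally, other clustered limits would serve. That bears on the choice of remedy, not on the need for one. None of these points makes the exact limit valid for the design the protocol permits.

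**Conclusion.** The concern holds. As written, the pivotal effectiveness rule does not guarantee its stated one-sided 0.025 level, because the only allowance for clustering lies outside the decision. Discreteness leaves little slack (0.0227 against 0.025).

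How far the level is exceeded is unknown. It is negligible if few subjects have more than one lesion, about 0.03 to 0.04 in the moderate mix C at correlations of 0.3 to 0.5, and up to 0.08 only in the stress case. All mixes and correlations are assumptions. The point should be fixed before analysis, but it does not show that the trial's result would be wrong.

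A separate, minor matter: the 72% goal was derived from per-patient rates (Protocol 7.8, SAP 3.2), and the documents do not say how it carries over to a per-lesion rate.

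**What to change.** - **Decision rule.** In SAP 3.4.2, and consistently in SAP 1.1 and 3.1 and in the protocol (Synopsis, 7.4, 7.10), make a subject-clustered lower 97.5% limit for the plain lesion proportion the deciding limit. A suitable choice is a GEE with independence working correlation, which is closed form, using the robust variance, K/(K−1) factor, t with K−1 degrees of freedom and logit scale shown above.
- **Fallback.** Use the exact limit if every subject has one lesion, or if all lesions succeed and the robust variance is zero.
- **Supportive analyses.** Report the exact lesion limit, the planned exchangeable GEE, and a subject-level analysis in which all of a subject's Target Lesions must succeed.
- **Sample size.** In SAP 3.2, Protocol 7.9 and the protocol synopsis, state that 101 and 113 treat lesions as independent, give the assumed lesions per subject, and reconcile 113 subjects with 113 Target Lesions.

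The cost is matched wording in both documents and a little programming. With one lesion per subject, nothing is lost. Otherwise power falls relative to the exact rule, which overstates the information. It can drop below 80% at a correlation of about 0.5 or more (0.78 in mix C at 0.5, 0.70 in mix D at 0.8), and the sample-size section should say so.

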#### 3.4.3 ANALYSIS OF THE SECONDARY ENDPOINT(S)

Binary endpoints will be analyzed with frequency counts and proportions. Exact binomial 95% confidence intervals will be used as descriptive measures. Time-to-event analyses may be employed as an additional descriptive analysis to account for partial follow-up, as applicable. Continuous endpoints will be summarized with mean, standard deviation, median, minimum, maximum, and number of

evaluable observations. Confidence intervals may be presented, where appropriate, using the t-distribution.

#### 3.4.4 SAFETY ANALYSES

Adverse Events (AEs) will be coded by Medical Dictionary for Regulatory Activities (MedDRA), calculated with each AE counted once only for a given participant and presented (severity, frequency, and relationship of AEs to study device and procedure) by System Organ Class (SOC) and preferred term groupings. The following information will be reported about each AE; start date, stop date, severity, relationship, expectedness, outcome, and duration.

Adverse events leading to premature discontinuation from the study intervention and serious treatment-emergent AEs will be presented in a listing.

#### 3.4.5 BASELINE DESCRIPTIVE STATISTICS

Descriptive statistics will be presented for clinically relevant baseline demographic, medical history, and clinical characteristic variables.

